# 3.2.4.3 Start of Open-Label Period

For subjects entering in the open-label period, the end of double-blind period date is the beginning of the open-label period date. All scheduled assessments occurring on this date are attributed to the double-blind period. The month 6 dose of ROMO is considered as occurring in the open-label period.

# 3.2.4.4 End of Open-Label Treatment Period date

End of OL Treatment Period date is defined as the date of the last assessment of the Month 12 visit. For subjects who discontinued from the study before completing Month 12, the ET date is used for the end of 12-month OL Treatment Period date. For those subjects who remained on study but missed the month 12 visit, last OL Treatment + 30 days will be used as the end of 12-month treatment period date.

# 3.2.4.5 End of Follow-Up Period date

End of FU Period date is defined as the date of the last assessment of the FU visit. For subjects who discontinued from the study before completing FU visit, the last contact date is used for the end of FU period date. For those subjects who remained on study but missed the FU, the final visit + 3 month or final administration of IMP + 4 month will be used as the end of FU period date.

# 3.3 Definition of Baseline values

A Baseline value for a subject is defined as the latest measurement for that subject up to and including the day of administration of first IMP, unless otherwise stated. If there is evidence that measurements taken on the same day as administration of first study medication were actually taken after this administration, then only values strictly prior to that date should be considered for that subject for baseline. If multiple measurements within the baseline period were done, the record that is the closest to and prior to or on the date of first IMP administration will be considered as the Baseline value. If a Baseline measurement is missing or not collected, and a Screening value (within 35 days prior to day 1) is available, the Screening value will be utilized as Baseline instead.

For computation of change from Baseline BMD of lumbar spine endpoint, Baseline will be identified as the average number of values (averaging is dedicated to the duplicate BMD values taken on the same day) obtained prior to the first dose of IMP (assuming that any observation on the same day as the first dose is prior to dosing, unless evidence stated). For computation of change from Baseline BMD of femoral neck and total hip, also other change from Baseline endpoints, the Baseline will be identified as the last observation prior to the first dose of IMP (assuming that any observation on the same day as the first dose is prior to dosing, unless evidence stated). The randomization date will be used as reference for subjects who did not receive any dose of IMP but who had non-missing observations on study.

Confidential Page 21 of 89

### 3.4 **Protocol deviations**

Important protocol deviations are deviations from the protocol which potentially could have a meaningful impact on study conduct or on the primary efficacy (effectiveness), key safety, or PK/PD outcomes for an individual subject. The criteria for identifying important protocol deviations will be pre-defined within the appropriate protocol-specific document. Important protocol deviations will be reviewed as part of the ongoing data cleaning process and data evaluation. All important deviations will be identified and documented prior to unblinding to confirm exclusion of subjects from analysis sets.

Since the PPS will be used for a sensitivity analysis of the primary endpoint which is assessed at Month 6, the exclusion from PPS is limited to the double-blind period, ie only study participants with IPD prior to Month 6 can be excluded from the PPS. Study participants with IPD after Month 6 will not be excluded from the PPS, but might be excluded from PK-PPS and PD-PPS during OLE Period.

### 3.5 **Analysis sets**

### 3.5.1 **Enrolled Set**

Enrolled Set (ES) will consist of subjects who signed the Informed Consent form (ICF).

### 3.5.2 Randomized Set

Randomized Set (RS) will consist of subjects who have been randomized. Disposition data are based on the ES and the RS.

### 3.5.3 Safety Set

Safety Set (SS) will consist of all randomized subjects who received at least 1 dose of IMP. These subjects will be analyzed according to the actual treatment received, where subjects who receive at least 1 dose of romosozumab will be analyzed in the romosozumab treatment group regardless of the randomized treatment.

Data on safety and exposure will be based on the SS.

### Full Analysis Set 3.5.4

The Full Analysis Set (FAS) will consist of all randomized subjects who received at least 1 dose of IMP and provided at least 1 Baseline and post-baseline BMD measurement. In the case of dosing administration error, analyses of the FAS will be conducted according to randomized treatment. This will be the primary efficacy analysis set.

The FAS will be used for demographics, disease characteristics and BMD efficacy analysis.

### Per-Protocol Set 3.5.5

The Per-Protocol Set (PPS) will consist of subjects in the FAS who have completed a minimal exposure of 6 months of a treatment regimen without any important protocol deviations that may linfluence the validity of the data for the primary and selected secondary BMD efficacy variables. Post-baseline deviations will not necessarily lead to exclusion of a subject from PPS analysis but may lead to exclusion of data.

The PPS will be used as supportive analyses for BMD efficacy analysis.

Confidential Page 22 of 89

### 3.5.6 Pharmacokinetic Per-Protocol Set

The Pharmacokinetic Per-Protocol Set (PK-PPS) will include all subjects in the SS who have at least one evaluable serum romosozumab concentration measurement with no further PK related important protocol deviations. This analysis set will be used in the PK analyses.

The Pharmacodynamic Per-Protocol Set (PD-PPS) will include all subjects in the SS who have at least 1 evaluable BTM measurement with no further PD-related important protocol device.

This analysis set will be used in the second device.

This analysis set will be used in the analyses of the BTMs.

### 3.6 Treatment assignment and treatment groups

It is expected that subjects will receive treatment as randomized; hence safety analyses will be based on the SS as randomized. However, if after unblinding it is determined that subjects received treatment other than what they were randomized to, then for safety analyses purposes subjects will be allocated to the actual treatment they received.

Treatment assignment for all other analysis sets will be according to randomization and not actual treatment received.

### **Center pooling strategy** 3.7

Based on the clusters of the sites with considerations of geographical and climate differences, the pooling strategy will consider the following 3 regions: North, East and South. The detail of site and corresponding region is listed in Appendix 13.9.

### **Coding dictionaries** 3.8

The latest version of Medical Dictionary for Regulatory Activities (MedDRA®) will be used to code all adverse events, medical histories, and concomitant diseases to a SOC and a PT.

World Health Organization (WHO) Drug dictionary will be used to code and classify all Prior / Concomitant Medications at the Anatomical Therapeutic Chemical Classification (ATC) level according to their indication and/or formulation.

### Changes to protocol-defined analyses 3.9

Section 13.6 of the protocol amendment 3 describes the primary and secondary analysis to be used in this study. More specifically, the protocol describes primary analysis using last observation carried forward (LOCF) as the method for handling missing data. This SAP has been modified such that the missing or out of window data due to COVID-19 impact will be imputed by multiple imputation and other missing data (rather than due to COVID-19 impact) will be imputed by LOCF. The original LOCF method will be also applied in sensitivity analysis. The modification is provided in this SAP.

Section 3.2.2 and Section 4.2.2.2 of the protocol amendment 3 describe the area under the curve through Month 12 in P1NP will be produced by treatment group (AUC). This SAP has removed AUC for other objectives.

Confidential Page 23 of 89

# 4 STATISTICAL/ANALYTICAL ISSUES

# 4.1 Adjustments for covariates

All model-based analyses will include treatment, age strata group (stratification factor), Baseline DXA BMD value, baseline machine type (Hologic or Lunar), region, the baseline machine type-by-baseline DXA BMD value interaction as independent variables, if applicable.

# 4.2 Handling of dropouts or missing data

In general, even if the IMP is discontinued, the subjects will be encouraged to continue the study schedule up to the planned final visit. For all subjects, all available data will be included in analyses, regardless of whether the data are collected before or after the subject discontinues IMP or before or after the subject takes alternative osteoporosis therapy (licensed drugs only) (see Appendix 13.1) or prohibited medication. This principle is as close as possible to the Intention to treat (ITT) principle and is currently accepted from a regulatory perspective as a conservative approach. Since this approach reflects effectiveness and real-world application rather than efficacy, it is in line with the late development stage of romosozumab within the clinical program.

If not otherwise specified, any missing data will not be imputed.

Supplementary analyses will be performed on the primary and secondary efficacy endpoints to assess the treatment effect of romosozumab when considering any subsequent or concomitant prohibited and/or alternative osteoporosis therapy (licensed drugs only).

Potentially, deaths could occur during this study. However, these events most likely will not be linked to the study indication of postmenopausal osteoporosis in China so that data which would have been collected after date of death will not be imputed.

In the data evaluation meetings (DEM), the following blinded overall incidences will be monitored since they have the potential to affect the interpretation or the existence of the BMD measurements:

- Incidence of subjects who discontinued IMP
- Incidence of subjects who discontinued IMP by reasons
- Incidence of subjects who received prohibited medication during ongoing IMP treatment
- Incidence of subjects who received alternative osteoporosis therapy during ongoing IMP treatment
- Incidence of subjects who received alternative osteoporosis therapy after early termination of IMP
- Incidence of subjects who died

For those sites which show strong deviations from the average of all sites during the DEM, appropriate measures such as re-training, following-up with corrective actions etc. would be considered. Further analyses including time to various discontinuation events (Kaplan-Meier plots), events by Baseline characteristics and events by efficacy endpoints may be conducted to explore the cause and impact of the discontinuations.

Confidential Page 24 of 89

Statistical Analysis Plan

**UCB** 

All the missing visit or missing data related to COVID-19 will be listed. Additional listings will be provided for the patients' assessments with COVID-19 impact. Additional summary and sensitivity analyses will be provided if deems necessary.

### 4.2.1 **Dates**

For analyses of AEs and concomitant medication usage, a complete date must be established in order to correctly identify the AE or medication as occurring during treatment in the study or not. For the purposes of imputing missing date or missing components of partially-reported start and stop dates for AEs and for medication use, the algorithms listed below will be followed. Start and stop dates of AEs or concomitant medication will be displayed as reported in the subject data. listings (ie, no imputed values will be displayed in data listings).

Missing start day, but month and year present:

If study start date (Day 1) occurred in the same month and year as the occurrence of the AE/medication, the start day of the event/medication will be assigned to the day of study start day.

Otherwise the start day will be set to the 1st day of the month.

Missing start day and month, but year present.

If the study start date (Day1) occurred in the same year as the occurrence of the AE/medication, the start day and month will be assigned to the date of study start day.

Otherwise the start day and month will be set to 01 Jan.

Missing end day, but month and year present:

If the date of last contact occurred in the same year and month as the occurrence of the AE/medication, the end day will be assigned to the date of the last contact.

Otherwise the end day will be set to the last day of the month.

Missing end day and month, but year present:

If the day of last contact occurred in the same year as the occurrence of the AE/medication, the end day and month will be assigned to the date of last contact.

Completely missing start date:

An AE will be considered as occurring during treatment.

Medications with an unknown stop date or a stop date after the date of the first IMP application will be considered as concomitant medication but not as prior medication. Medications with a stop date prior to first IMP application will be considered as prior medication but not as concomitant medication.

Completely missing stop date:

Adverse events with a completely missing stop date will be considered ongoing.

Medications with a completely missing stop date will be considered as concomitant medications.

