11.1.1.1 Adverse event

An AE is any untoward medical occurrence in a patient or clinical investigation subject administered a pharmaceutical product that does not necessarily have a causal relationship with this treatment. An AE can therefore be any unfavorable and unintended sign (including an abnormal laboratory finding), symptom, or disease temporally associated with the use of a medicinal (investigational) product, whether or not related to the medicinal (investigational) product.

In order to ensure complete safety data collection, all AEs occurring during the study (ie, after the signing of the ICF), including any pretreatment and posttreatment periods required by the protocol, must be reported in the eCRF even if no IMP was taken but specific study procedures were conducted. This includes all AEs not present prior to the initial visit and all AEs that recurred or worsened after the initial visit.

Signs or symptoms of the condition/disease for which the IMP is being studied should be recorded as AEs only if their nature changes considerably or their frequency or intensity increases in a clinically significant manner as compared to the clinical profile known to the investigator from the subject's history or the Baseline Period.

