#### Adverse events c 10.2

Treatment emergent AEs (TEAE) are defined as all AEs started or worsened in severity on or after the date of receiving first dose of IMP and before EOS date except lipid-type AEs starting on the date of first dose of IMP and not worsening (and not deemed IMP related by the investigator). Lipid-type AEs will be defined by the Dyslipidaemia SMQ (see Appendix 13.7). The different handling of lipid-type AEs starting on the date of first dose of IMP is to ensure that pre-existing lipid abnormalities are not reported as TEAEs (lipids are only measured at Day 1 before first IMP and not at Screening).

All subsequently described displays in Section 10.2 will be compiled for the DBPC Period and for the overall study period (treatment start through Month 15). For the displays on the DBPC Period, TEAEs with a start date before or on the End of DBPC period date will be included. For the overall period, TEAEs with a start date before or on the EOS date will be included.

Duration of AEs will not be calculated if there is missing stop date information. If the intensity of an AE is unknown, it is considered as severe. If the relationship to study drug is missing, it is considered as related. Note that if the seriousness of an adverse event is unknown, every attempt should be made to resolve this prior to a snapshot for an interim analysis or database lock; in the exceptional case that the seriousness of an adverse event is still missing then no imputation should be applied for this characteristic.

If a TEAE occurs on the date of switch from the DBPC period to the OL period, the event is attributed to the DBPC treatment. The only exception that TEAEs of injection site reactions (see Appendix 13.5), potentially related to hypersensitivity (Standardized MedDRA® Query [SMQ], narrow scope) will be in OL period.

The number and incidence of TEAEs will be summarized by treatment group, the MedDRA® SOC and PT with the SOC sorted alphabetically and within SOC the PT sorted by descending order of frequencies. The incidence of TEAEs will also be summarized by treatment group (including romosozumab total), intensity and relationship to IMP.

Adverse events will be presented as "number of participants (percentage of participants) [number of events]". In this style of output, "[number of events]" will include all cases of an AE including repeat occurrences in individual participants, while "number of participants" will count each participant only once.

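### SAP 4.2.1 imputes partial adverse event onsets without checking a recorded stop date, so an event known to have ended before the first dose can be counted as treatment-emergent.

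*SAP*

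**What the plan says.** SAP 4.2.1 (Dates) imputes partial start dates by comparison with Day 1 only.

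- Day missing, month and year as Day 1: "the start day of the event/medication will be assigned to the day of study start day". Any other month goes to its first day.
- Day and month missing, year as Day 1: "the start day and month will be assigned to the date of study start day". For any other year: "Otherwise the start day and month will be set to 01 Jan".
- Start completely missing: "An AE will be considered as occurring during treatment".

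The same section does apply a stop-date test to medications whose start is completely missing: "Medications with a stop date prior to first IMP application will be considered as prior medication but not as concomitant medication". It has no counterpart for adverse events.

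SAP 10.2 then makes an event treatment-emergent if it started or worsened on or after the first dose and before the end-of-study date, with one exception for lipid events starting on Day 1. For the double-blind displays, "TEAEs with a start date before or on the End of DBPC period date will be included".

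Protocol 11.1.1.1 requires reporting of "all AEs occurring during the study (ie, after the signing of the ICF), including any pretreatment and posttreatment periods", and Protocol 5.1 allows Screening to run from Day -35. Events before the first dose are therefore in the database.

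**The concern.** Sending an ambiguous onset to Day 1 is a normal, cautious default, because it avoids losing a possible treatment-emergent event. The default has no justification once the stop date shows that the event was over before any IMP was given. The imputed record is then impossible (it starts after it ends), and the TEAE table counts an event that cannot have emerged on treatment.

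SAP 10.2 shows that the plan wants to avoid this: its lipid exception exists to keep pre-existing abnormalities out of the TEAE counts. What is at stake is the accuracy of the TEAE tables, chiefly in sparse categories where one event is visible.

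**Working it through.** There is no stated figure to reproduce. The check applies the SAP 4.2.1 and 10.2 rules to example dates.

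**Stop-date defect.** Take Day 1 = 20 Mar 2021 and a recorded stop of 12 Mar 2021, inside the 35-day Screening window.

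| Onset as recorded | Imputed start | TEAE under SAP 10.2? | Consistent with the stop date? |
|---|---|---|---|
| `-- Mar 2021` | 20 Mar 2021 | Yes | No, start is 20 - 12 = 8 days after stop |
| `2021` only | 20 Mar 2021 | Yes | No, same 8 days |
| completely missing | none; taken as on treatment | Yes | No |
| `-- Feb 2021` | 1 Feb 2021 | No | Yes |

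The error is confined to onsets that share Day 1's month (or its year, if only the year is known) and to completely missing starts. If the stop falls on or after Day 1, an imputed start of Day 1 does not exceed it, so a stop-date bound changes nothing there. With the bound, the first three rows become not treatment-emergent.

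The bound would not lose an event that later worsened. Protocol 11.1.2.2 has a worsening recorded as a repeated event, which carries its own dates.

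**Size.** The documents give neither the number of Screening events nor the number of partial dates. Assume 30 to 60 Screening events with 2% to 5% partial onsets. That gives 30 × 0.02 = 0.6 to 60 × 0.05 = 3 Screening events with a partial onset. This is a ceiling under those assumptions, since only those that meet the conditions above and also stopped before the first dose are affected.

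**Secondary note: crossover.** With the same Day 1 and Month 6 taken as Day 180, crossover is 20 Mar + 179 days = 15 Sep 2021.

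- True onset 20 Sep, recorded `-- Sep 2021`: imputed to 1 Sep, so placed in the double-blind displays.
- Recorded `-- Oct 2021` or `-- Nov 2021`: imputed to the first of that month, correctly open-label.
- Recorded `2021` only: imputed to 20 Mar 2021, so double-blind. Recorded `2022` only: 1 Jan 2022, correctly open-label.
- With Day 1 = 1 Oct 2021 instead, crossover is 29 Mar 2022, and `2022` only is imputed to 1 Jan 2022, so double-blind.

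For day-missing onsets, the share of open-label events moved depends on the days left in the crossover month. Averaged over a 365-day year, that is (7 × 465 + 4 × 435 + 378) / 365 = 5,373 / 365 = 14.7 days. With onset uniform over 180 open-label days, 14.7 / 180 = 8.2%. Full enumeration of Day 1 over one year gives the same 8.2%, 75% for year-only onsets, and 0% moving from double-blind to open-label.

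**The case against.** The strongest case on the other side concerns size and visibility. Adverse events are asked about at every monthly visit through Month 12, so partial onsets should be uncommon and year-only onsets rare. The rule is the same in both arms. SAP 10.2.3 plans no statistical testing of safety. Listings show dates as reported, so a reader could see a partial onset beside an earlier stop. All of this stands, and it is why few events are expected. None of it justifies overriding a stop date that is known.

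Four stronger readings are tempting, and the documents do not support them.

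- A reader might infer that open-label events with partial onset in placebo women are generally counted as placebo events. With only the day missing, just the crossover month is affected, so about 92% (100 - 8.2) stay in open-label. The overall-period tables keep all of them in the placebo/romosozumab group.
- A reader might infer that such onsets should be moved to open-label for placebo women. That would treat the arms differently within the randomized comparison. It would also remove true double-blind events: on average 5,738 / 365 = 15.7 double-blind days fall in the crossover month, and 15.7 / 180 = 8.7% of day-missing double-blind onsets lie there.
- A reader might infer that a year-only start of alternative osteoporosis therapy deletes all of a woman's post-baseline BMD in Supplementary analyses 2 and 3. SAP 4.2.1 gives its purpose as deciding whether an event or medication occurred during treatment, and no text makes it the cut-off for that intercurrent event. Appendix 13.1 sends these patients to medical review at the data evaluation meetings. A stop-date bound would not correct a start dated too early in any case.
- A reader might take the share of Screening onsets falling in Day 1's month (42% with a 35-day window and uniform onset) as the size of the defect. It is not, because it includes events still ongoing at Day 1, for which the default is reasonable.

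**Conclusion.** The stop-date point holds as a gap in a stated rule. A Screening event with onset known only to the Day 1 month or year, or with no start date, is counted as a TEAE even when its recorded stop precedes the first dose. No other section of the SAP or protocol corrects this. The effect should be very small: at most about 0.6 to 3 events under the assumed Screening counts and partial-date rates, which do not come from the documents.

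The crossover effect is real but secondary. It reaches only the double-blind displays and, for day-missing onsets, only the crossover month. It can only add open-label events to the double-blind columns, never the reverse. That conclusion assumes crossover at Day 180, and the 8.2% also assumes uniform onset. Because any reassignment rule also moves some true double-blind events, the handling of these onsets is a trade-off to settle openly and not a clear error.

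**What to change.** Add two statements to SAP 4.2.1:

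1. An imputed adverse event start date may not be later than a recorded stop date.
2. An adverse event with a recorded stop date before the first IMP dose is not treatment-emergent, whether its start date is partial or completely missing. A partial stop date counts for this only if the latest date it allows is before the first dose.

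For crossover, if the team wants a rule, state one that uses the recorded stop date and is identical in both arms. An event that stopped before the first open-label dose stays in the double-blind period. For onsets that remain ambiguous, choose one period for both arms and acknowledge which true events that choice displaces.

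The cost is a few sentences and a few lines of derivation code. No efficacy analysis changes.
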